15.2 Appendix 2: Response Criteria

Response criteria for subjects with solid tumors and measurable disease

Anti-tumor activity will be assessed based on clinical evidence and the Response Evaluation Criteria in Solid Tumors (RECIST) Version 1.1 criteria for solid tumors ([Eisenhauer, 2009](#)).

Evaluation of Target Lesions

Definitions for assessment of response for target lesion(s) are as follows:

- Complete Response (CR): Disappearance of all target lesions. Any pathological lymph nodes must be <10 mm in the short axis.
- Partial Response (PR): At least a 30% decrease in the sum of the diameters of target lesions, taking as a reference, the baseline sum of the diameters (e.g. percent change from baseline).
- Stable Disease: Neither sufficient shrinkage to qualify for PR nor sufficient increase to qualify for progressive disease.
- Progressive Disease (PD): At least a 20% increase in the sum of the diameters of target lesions, taking as a reference, the smallest sum of diameters recorded since the treatment started (e.g. percent change from nadir, where nadir is defined as the smallest sum of diameters recorded since treatment start). In addition, the sum must have an absolute increase from nadir of 5 mm.
- Not Applicable (NA): No target lesions at baseline.
- Not Evaluable (NE): Cannot be classified by one of the five preceding definitions.

Note:

- If lymph nodes are documented as target lesions the short axis is added into the sum of the diameters (e.g. sum of diameters is the sum of the longest diameters for non-nodal lesions and the short axis for nodal lesions). When lymph nodes decrease to non-pathological size (short axis <10 mm) they should still have a measurement reported in order not to overstate progression.
- If at a given assessment time point all target lesions identified at baseline are not assessed, sum of the diameters cannot be calculated for purposes of assessing CR, PR or stable disease or for use as the nadir for future assessments. However, the sum of the diameters of the assessed lesions and the percent change from nadir should be calculated to ensure that progression has not been documented. If an assessment of PD cannot be made, the response assessment should be NE.
- All lesions (nodal and non-nodal) should have their measurements recorded even when very small (e.g. 2 mm). If lesions are present but too small to measure, 5 mm should be recorded and should contribute to the sum of the diameters, unless it is likely that the lesion has disappeared in which case 0 mm should be reported.
- If a lesion disappears and reappears at a subsequent time point it should continue to be measured. The response at the time when the lesion reappears will depend upon the status of the other lesions. For example, if the disease had reached a CR status then PD would be documented at the time of reappearance. However, if the response status was PR or

stable disease the diameter of the reappearing lesion should be added to the remaining diameters and response determined based on percent change from baseline and percent change from nadir.

Evaluation of Non-target Lesions

Definitions for assessment of response for non-target lesions are as follows:

- Complete Response (CR): The disappearance of all non-target lesions. All lymph nodes identified as a site of disease at baseline must be non-pathological (e.g. <10 mm short axis).
- Non-CR/Non-PD: The persistence of 1 or more non-target lesion(s) or lymph nodes identified as a site of disease at baseline ≥ 10 mm short axis.
- Progressive Disease (PD): Unequivocal progression of existing non-target lesions.
- Not Applicable (NA): No non-target lesions at baseline.
- Not Evaluable (NE): Cannot be classified by one of the four preceding definitions.

Note:

- In the presence of measurable disease, progression on the basis of solely non-target disease requires substantial worsening such that even in the presence of stable disease or PR in target disease, the overall tumor burden has increased sufficiently to merit discontinuation of therapy.
- Sites of non-target lesions, which are not assessed at a particular timepoint based on the assessment schedule, should be excluded from the response determination (e.g. non-target response does not have to be "Not Evaluable").

New Lesions

New malignancies denoting disease progression must be unequivocal. Lesions identified in follow-up in an anatomical location not scanned at baseline are considered new lesions.

Any equivocal new lesions should continue to be followed. Treatment can continue at the discretion of the investigator until the next scheduled assessment. If at the next assessment the new lesion is considered to be unequivocal, progression should be documented.

Evaluation of Overall Response

Table 15-1 presents the overall response at an individual time point for all possible combinations of tumor responses in target and non-target lesions with or without the appearance of new lesions for subjects with measurable disease at baseline.

Table 15-1 Evaluation of Overall Response for Subjects with Measurable Disease at Baseline

Target Lesions	Non-Target Lesions	New Lesions	Overall Response
CR	CR or NA	No	CR
CR	Non-CR/Non-PD or NE	No	PR
PR	Non-PD or NA or NE	No	PR
Stable disease	Non-PD or NA or NE	No	SD

NE	Non-PD or NA or NE	No	NE
PD	Any	Yes or No	PD
Any	PD	Yes or No	PD
Any	Any	Yes	PD

CR=complete response, PR = partial response, PD=progressive disease, NA= not applicable, and NE=not evaluable

Note:

- Subjects with a global deterioration of health status requiring discontinuation of treatment without objective evidence of disease progression at that time should be classified as having "symptomatic deterioration." Objective response status is determined by evaluations of disease burden. Every effort should be made to document the objective progression even after discontinuation of treatment.
- In some circumstances, it may be difficult to distinguish residual disease from normal tissue. When the evaluation of CR depends on this determination, it is recommended that the residual lesion be investigated (fine needle aspirate/biopsy) to confirm the CR.

Evaluation of Best Overall Response

The best overall response is the best response recorded from the start of the treatment until disease progression/recurrence and will be determined programmatically by Novartis based on the investigators assessment of response at each time point.

- To be assigned a status of stable disease, follow-up disease assessment must have met the SD criteria at least once after first dose of study medication at a minimum interval of 12 weeks.
- If the minimum time for stable disease is not met, best response will depend on the subsequent assessments. For example if an assessment of PD follows the assessment of stable disease and stable disease does not meet the minimum time requirement the best response will be PD. Alternative subjects lost to follow-up after a stable disease assessment not meeting the minimum time criteria will be considered not evaluable.

Confirmation Criteria:

- To be assigned a status of PR or CR, a confirmatory disease assessment should be performed at Week 16 if initial response was seen at the Week 8 scan. Initial responses (CR/PR) that occur Week 16 or after should be confirmed not less than 4 and not more than 8 weeks after the criteria for response are first met.

Response Assessment in Neuro-oncology (RANO) criteria (Glioma Subjects)

Anti-tumor activity will be assessed based on clinical evidence and the Response Assessment in Neuro-Oncology (RANO) criteria for solid tumors ([Wen, 2010](#)).

NOTE: *As part of Protocol Amendment V11, the revised RANO criteria for LGG (RANO-LGG; [Wen, 2017](#)) will be used for central independent review. This review is in addition to the previously performed review using RANO ([Wen, 2010](#)). These criteria are noted in [section 15.2](#).*

All measurable and nonmeasurable lesions should be assessed using the same techniques as at baseline. Ideally, subjects should be imaged on the same MRI scanner, or at least with the same magnet strength, for the duration of the study to reduce difficulties in interpreting changes.

Measurable disease is defined as bidimensionally contrast enhancing lesions with clearly defined margins by CT or MRI scan, with two perpendicular diameters of at least 10 mm, visible on two or more axial slices that are preferably, at most, 5 mm apart with 0-mm skip. As with RECIST version 1.1, in the event the MRI is performed with thicker slices, the size of a measurable lesion at baseline should be two times the slice thickness. In the event there are interslice gaps, this also needs to be considered in determining the size of measurable lesions at baseline. Measurement of tumor around a cyst or surgical cavity represents a particularly difficult challenge. In general, such lesions should be considered nonmeasurable unless there is a nodular component measuring ≥ 10 mm in diameter. The cystic or surgical cavity should not be measured in determining response.

Nonmeasurable disease is defined as either unidimensionally measurable lesions, masses with margins not clearly defined, or lesions with maximal perpendicular diameters less than 10 mm.

Radiographic response should be determined in comparison to the tumor measurements obtained at pretreatment baseline for determination of response, the smallest tumor measurements at either pretreatment baseline or after initiation of therapy should be used for determination of progression.

- Complete response (CR): Complete disappearance of all enhancing measurable and nonmeasurable disease on contrast enhanced MRI scan sustained for at least 4 weeks, no new lesions, and stable or improved nonenhancing (T2/FLAIR) lesions. In addition, subject must be off steroids or only on physiologic replacement doses. In the absence of a confirming scan 4 weeks later, this response will be considered only stable disease.
- Partial response (PR): Greater than or equal to a 50% reduction, compared to baseline, in the sum of products of the perpendicular diameters for all measurable lesions for at least 4 weeks, no progression of nonmeasurable disease, no new lesions, and stable or improved nonenhancing (T2/FLAIR) lesions. In addition, subject must be on a corticosteroid dose not greater than the dose at the time of baseline scan and be stable or improving clinically. In the absence of a confirming scan 4 weeks later, this response will be considered only stable disease.
- Progressive Disease (PD): Greater than or equal to a 25% increase in sum of the products of perpendicular diameters of enhancing lesions (compared with baseline if no decrease) on stable or increasing doses of corticosteroids, OR a significant increase in T2/FLAIR nonenhancing lesions on stable or increasing doses of corticosteroids compared with baseline scan or best response after initiation of therapy, not due to comorbid events, OR the appearance of any new lesions, OR clear progression of nonmeasurable lesions, OR definite clinical deterioration not attributable to other causes apart from tumor, or to decrease in corticosteroid dose. Failure to return for evaluation as a result of death or deteriorating condition should also be considered as progression.
- Stable disease: If subject does not qualify for CR, PR, or PD and has stable nonenhancing (T2/FLAIR) lesions on same or lower doses of corticosteroids compared with baseline scan and clinically stable status. In the event that the corticosteroid dose was increased for

new symptoms and signs without confirmation of disease progression on neuroimaging and subsequent follow-up imaging shows that this increase in corticosteroid dose was required because of disease progression, the last scan considered to show stable disease will be the scan obtained when the corticosteroid dose was equivalent to the baseline dose.

Increase in corticosteroid dose alone, in the absence of clinical deterioration related to tumor, will not be used as a determinant of progression. Subjects with stable imaging studies whose corticosteroid dose was increased for reasons other than clinical deterioration related to tumor do not qualify for stable disease or progression. They should be observed closely. If their corticosteroid dose can be reduced back to baseline, they will be considered as having stable disease; if further clinical deterioration related to tumor becomes apparent, they will be considered to have progression. The date of progression should be the first time point at which corticosteroid increase was necessary.

The definition of clinical deterioration is left to the discretion of the treating physician, but it is recommended that a decline in the KPS from 100 or 90 to 70 or less, a decline in KPS of at least 20 from 80 or less, or a decline in KPS from any baseline to 50 or less, for at least 7 days, be considered neurologic deterioration unless attributable to comorbid events or changes in corticosteroid dose. Similarly, a decline in the Eastern Cooperative Oncology Group and WHO performance scores from 0 or 1 to 2 or 2 to 3 would be considered neurologic deterioration.

Subjects with nonmeasurable enhancing disease whose lesions have significantly increased in size and become measurable (minimal bidirectional diameter of ≥ 10 mm and visible on at least two axial slices that are preferably, at most, 5 mm apart with 0-mm skip) will also be considered to have experienced progression. The transition from a nonmeasurable lesion to a measurable lesion resulting in progression can theoretically occur with relatively small increases in tumor size (e.g., a 9 X 9mm lesion [nonmeasurable] increasing to a 10 X 11mm lesion [measurable]). Ideally, the change should be significant (>5 mm increase in maximal diameter or $\geq 25\%$ increase in sum of the products of perpendicular diameters of enhancing lesions).

In general, if there is doubt about whether the lesion has progressed, continued treatment and close follow-up evaluation will help clarify whether there is true progression. If there is uncertainty regarding whether there is progression, the patient may continue on treatment and remain under close observation (e.g., evaluated at 4-week intervals). If subsequent evaluations suggest that the patient is in fact experiencing progression, then the date of progression should be the time point at which this issue was first raised.

Response assessment in neuro-oncology (RANO) criteria for low-grade gliomas (LGG) (RANO-LGG).

During the course of the trial, revised RANO criteria specific for LGG have become available (RANO-LGG; [Wen, 2017](#)). These criteria will also be used for central independent review per Protocol Amendment v11. This review is in addition to the previously performed review using RANO ([Wen, 2010](#)).

According to the updated RANO-LGG criteria, the definition of measurable disease is modified. Measurable disease is defined as bidimensionally visible lesions on T2 weighted fluid-attenuated inversion recovery (FLAIR) scans with clearly defined margins, with two perpendicular diameters of at least 10 mm (or at least two slice thicknesses with no gaps

between slices), visible on two or more axial slices that are preferably, at most, 5 mm apart with 0mm skip.

Non-measurable disease includes all other lesions, including:

- unidimensionally measurable lesions
- lesions with maximal perpendicular diameter that is both < 10mm and less than two slice thicknesses with no gaps between slices
- lesions with borders that cannot be reproducibly measured
- dural, bony skull metastases
- cystic or necrotic lesions (without a nodular component)
- other measurable lesions that cannot be considered as target lesions

Lesions composed of a tumor around a cyst or a surgical cavity are considered non-measurable unless there is a nodular component that measures 10 mm or more in 2 perpendicular diameters. The cystic or surgical cavity should not be measured for the determination of a response. Non-measurable lesions should all be followed as non-target lesions.

Target lesions should be assessed quantitatively at each of the time points specified in the protocol.

The updated response criteria for LGG are defined in the following tables. Please note that the minor response category is not used in this clinical trial. Patients meeting criteria for minor response will be considered to have stable disease for the purposes of this trial.

Response assessment of target lesions

Response Criteria	Evaluation of target lesions
Complete response (CR)	Complete disappearance of all measurable lesions on T2/FLAIR images sustained for at least 4 weeks.* No new or increased enhancement on T1 images.
Partial response (PR)	≥ 50% decrease, compared with baseline, in the sum of products of perpendicular diameters of all measurable lesions on T2/FLAIR sustained for at least 4 weeks.* No new or increased enhancement on T1 images.
Progressive disease (PD)	≥25% increase in sum of the products of perpendicular diameters of measurable lesions on T2/FLAIR images compared to nadir. Increased enhancement on T1 images showing evidence of malignant transformation.
Stable disease (SD)	Neither sufficient shrinkage to qualify for partial response nor sufficient increase to qualify for progressive disease. No new or increased enhancement on T1 images.
Not Evaluable (NE)	Not evaluable will be used in exceptional cases where one or more measurable lesions cannot be assessed or have been assessed using a different method than baseline, in absence of progressive disease documentation
* In the absence of a confirming scan 4 weeks later, this scan will be considered only stable disease.	

Response assessment of non-target lesions

Response Criteria	Evaluation of non-target lesions
Complete response (CR)	Complete disappearance of all non-measurable lesions on T2/FLAIR. No new or increased enhancement on T1 images.
NonCR/NonPD	Persistence of one or more non-measurable lesions on T2/FLAIR. No new or increased enhancement on T1 images.
Progressive disease (PD)	Significant and unequivocal increase of the non-measurable lesions on T2/FLAIR or increase of enhancement on T1 images
Not Evaluable (NE)	Not evaluable will be used in exceptional cases where one or more non-measurable lesions cannot be assessed or have been assessed using a different method than baseline, in absence of progressive disease documentation

A lesion not present at baseline and appearing at any follow-up evaluation timepoint (TP) is considered a New Lesion.

The Investigator/local reader will characterize each new lesion as either equivocal or unequivocal (progressive disease). If unsure of a new lesion, the Investigator/local reader will mark it as equivocal and assess at the next timepoint if the lesion is present. Appearance of an equivocal new lesion does not lead to a determination of PD. If repeat scans confirm the lesion is unequivocal, progression should be retrospectively assigned back to the first observation of the lesion.

The evaluation of overall lesion response at each assessment is a composite of the target lesion response, non-target lesion response, the presence of new lesions, corticosteroid use relative to baseline, and clinical status as assessed by investigator and supported by the ECOG/Karnofsky Performance Scale as shown below

Overall lesion response at each assessment (measurable and non-measurable disease at baseline)

Criterion	Complete Response	Partial Response	Stable Disease	Progressive Disease
T2/FLAIR (target lesions)	None	≥50% decrease in SPPD compared to baseline	<50% decrease Compared to baseline but <25% increase in SPPD compared to Nadir	≥25% increase in SPPD compared to Nadir**
T2/FLAIR (non-target lesions)	None	Stable or improved	Stable or improved	Unequivocal PD**

Criterion	Complete Response	Partial Response	Stable Disease	Progressive Disease
T1 gadolinium enhancing disease	Stable or improved	Stable or improved	Stable or improved	Unequivocal increase**
New Lesions	None	None	None	Present*
Corticosteroids compared to baseline	None	Stable or decreased	Stable or decreased	NA***
Clinical Status compared to baseline	Stable or improved	Stable or improved	Stable or improved	Worsened**
Requirement for Response	All	All	All	Any**

Complete Response (CR):

All of the following criteria must be met:

- a. Complete disappearance of the lesion of T2 or FLAIR imaging. . In the absence of a confirming scan at least 4 weeks later, this scan will be considered only stable disease.
- b. No new lesions, no new T2 or FLAIR abnormalities apart from those consistent with radiation effects, and no new or increased size of enhancement
- c. Participants must be on no steroids or on physiologic replacement doses only.
- d. Stable or improved clinically, for clinical signs and symptoms present at baseline and recorded to be disease related

Partial Response (PR):

All of the following criteria must be met:

- a. Greater than or equal to 50% in the product of perpendicular diameters of the lesion on T2 or FLAIR imaging sustained for at least 4 weeks compared with baseline.
- b. No new lesions, no new T2 or FLAIR abnormalities apart from those consistent with radiation effects, and no new or increased size of enhancement
- c. Patients should be on a corticosteroid dose that should not be greater than the dose at time of baseline scan, and should be stable or improved clinically.

Stable Disease (SD):

All of the following criteria must be met:

- a. Does not qualify for CR, PR, MR or progression.
- b. Stable area of non-enhancing abnormalities on T2 or FLAIR imaging
- c. No new lesions, no new T2 or FLAIR abnormalities apart from those consistent with radiation effects, and no new or increased size of enhancement
- d. Patients should be on a corticosteroid dose that should not be greater than the dose at time of baseline scan, and should be stable or improved clinically.

Progressive Disease (PD):

- a. A 25% increase of the T2 or FLAIR non-enhancing lesion on stable or increasing doses of corticosteroids compared with nadir, not attributable to radiation effect or to comorbid events
- b. Significant and unequivocal increase of the non-measurable lesions on T2/FLAIR
- c. Development of new lesions or increased size of enhancement
- d. Definite clinical deterioration not attributable to other causes apart from the tumor, or decrease in corticosteroid dose
- e. Failure to return for evaluation because of death or deteriorating condition, unless caused by documented non-related disorders.

If there is uncertainty regarding whether there is progression, the patient may continue on treatment and remain under close observation (e.g., evaluated at 4-week intervals). If subsequent evaluations suggest that the patient is in fact experiencing progression, then the date of progression should be the time point at which this issue was first raised.

Response Status Unknown: Not Evaluable (NE):

- a. Progressive disease has not been documented and one or more target or non-target lesions have not been assessed.
- b. Change in method or technique for assessing target and non-target lesions as that used at baseline regardless of the justification of the change; e.g. if a participant develops a contraindication to MRI intravenous (IV) contrast media during the trial, a non-contrast MRI of the brain can be used (if possible); the participants response should only be recorded as not evaluable or progressive disease.

Definition of disease state, response criteria and response definition for LCH

Adapted from Histiocyte Society Evaluations and Treatment Guidelines, April 2009.

Definition of Disease State

NON ACTIVE DISEASE (NAD)	no evidence of disease	resolution of all signs or symptoms
ACTIVE DISEASE	regressive disease	regression of signs or symptoms, no new lesions*
	stable disease	persistence of signs of symptoms, no new lesions
	progressive disease	progression of signs or symptoms and/or appearance of new lesions**

*Plus partial or complete response by RECIST (Eisenhauer, 2009); and/or pulmonary criteria if applicable

** Isolated pulmonary LCH: improvement in lung function is >10% increase in baseline FEV1 or DLCO at time of disease assessment. Disease progression is >15% decline from baseline FEV1 or DLCO or FVC OR progression of symptoms (dyspnea, cough, constitutional symptoms) that cannot be explained by diagnoses other than pulmonary LCH (infection, heart disease, and/or other clinical issues excluded by careful clinical evaluation and testing)

** Isolated bone disease: progression is defined as appearance of new bone lesions or lesions in other organs

Response Criteria

BETTER	Complete Resolution	NAD
	Regression	AD Better
INTERMEDIATE	Mixed	New lesions in one site, regression in another site
	Stable	Unchanged
WORSE	Progression	

Response Definition for Efficacy

	3 Month Assessment	6 Month Assessment (performance relative to 3 month assessment)
Response	NAD or AD Better Mixed Stable	NAD or AD Better or Stable NAD or AD Better NAD or AD Better
Failure	NAD or AD Better NAD or AD Better Mixed or Stable ^a Progression	Mixed Progression Mixed or Stable ^a or Progression N/A

NAD = Non Active Disease

AD = Active Disease

Stable = Unchanged

Mixed = New lesions in one site, regression in another site

^a Subjects who are assessed only as stable at the 3 and 6 month assessment are not considered a treatment response; however, they may be considered for continued treatment

LCH Scoring System (Donadieu, 2004)

Variable	Modality	Score
Bone (a)	Pain	1
	No Pain	0
Bone (b)	Compressing other organs (orbit or spine)	2
	No compression	0
Fever (>38.5°C)	Yes	1
	No	0
Lung: iconography	Pneumothorax	2
	Interstitial lesion on chest x-ray or lung CT	1
	Normal chest x-ray or lung CT	0
Lung: function	Mechanical ventilation or PFT >50%	5
	Supplemental oxygen or PFT between 50 and 80%	2
	No dysfunction, no cyanosis, no supplemental oxygen	0
Skin: area	25%	2
	5-25%	1
	Below 5%	0
Soft tissue tumor (including CNS)	5 cm maximum diameter	2
	2-5 cm maximum diameter	1

Variable	Modality	Score
	0-2 cm maximum diameter	0
Nodes (>2 cm)	Yes	1
	No	0
Liver	Below umbilicus	2
	Enlarged, above umbilicus	1
	Not enlarged	0
Spleen	Below umbilicus	2
	Enlarged, above umbilicus	1
	Not enlarged	0
Liver (enzymes)	>10 ULN	2
	3-10 ULN	1
	<3 ULN	0
Liver (gamma GT)	>10 ULN	2
	3-10 ULN	1
	<3 ULN	0
Albumin	Perfusion required in past week	3
	No perfusion but <30 g/L	1
	>30 g/L	0
Platelet: requirements in past week	More than two transfusions	4
	1 or 2 transfusions	3
	Low platelet count, no transfusion	2
	Normal count	0
Red cells: requirements in past week	More than 2 U	4
	1 or 2 U	3
	Hgb below 10 g/dL, no transfusion	1
	No transfusion	0

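### The RANO-LGG criteria in Protocol Appendix 2 set about three incompatible thresholds for when increased T1 enhancement is progression, and leave some scans with no category

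*Protocol*

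**What the plan says.** Amendment 11 added RANO-LGG criteria to Protocol Section 15.2 for an additional independent review of LGG patients; the review under the older RANO criteria is kept. The appendix gives the enhancement rule for PD four times:

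- Target-lesion table, PD row: 25% growth on T2/FLAIR, followed by "Increased enhancement on T1 images showing evidence of malignant transformation". No and/or joins the two sentences.
- Non-target table, PD row: "Significant and unequivocal increase of the non-measurable lesions on T2/FLAIR or increase of enhancement on T1 images".
- Overall-response table, T1 row, PD column: "unequivocal increase".
- Closing PD list, item c: "Development of new lesions or increased size of enhancement".

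The other categories exclude any rise. The target-table SD row reads "Neither sufficient shrinkage to qualify for partial response nor sufficient increase to qualify for progressive disease. No new or increased enhancement on T1 images", and its CR and PR rows carry the same bar. In the overall table, CR, PR and SD all need enhancement that is stable or better. The closing CR, PR and SD lists each require "no new or increased size of enhancement". The not-evaluable row is narrow: "Not evaluable will be used in exceptional cases where one or more measurable lesions cannot be assessed", or were assessed by a different method from baseline.

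SAP Section 2.6.1 says only that the updated criteria will be used for independent review of LGG. Neither document says which of the four statements governs.

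**The concern.** RANO-LGG was brought in because the older criteria suit non-enhancing low-grade glioma poorly, so the handling of enhancement is central to the new read. As written, two careful readers can classify the same scan differently, and one reader may find no category for it. The appendix closes comparable gaps elsewhere: an equivocal new lesion is expressly not PD, and minor response is expressly SD. Enhancement has no such rule.

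Timing matters too. Part 2 enrolment is closed, the older-criteria review has been performed, and LGG data were analysed at the interim described in Protocol Section 5.3.2. A threshold settled during or after the read would be chosen with earlier results already known.

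**Working it through.** The plan gives no figure on this point to reproduce. The check applies each statement, as written, to hypothetical scans. Assumptions: all lesions assessed by the baseline method, no new lesions, steroids and clinical status stable, non-measurable disease present and stable, T2/FLAIR product unchanged, and the two target-table PD conditions read as alternatives.

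| Scan | Target table | Non-target table | Overall table | Closing list |
|---|---|---|---|---|
| No increase in enhancement | SD | non-CR/non-PD | SD | SD |
| Equivocal increase, no transformation | no category | PD on plain reading; no category if the unequivocal qualifier also covers enhancement | no category | PD |
| Unequivocal increase, no transformation | no category | PD | PD | PD |
| Unequivocal increase with transformation | PD | PD | PD | PD |

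For the second and third rows, the target table fails in the same way: CR, PR and SD are barred by the increase, PD needs transformation, and not-evaluable does not apply because the lesions were assessed by the same method. Repeating the exercise with a 60% T2/FLAIR decrease leaves both rows unchanged; only the no-increase scan differs, becoming PR in the target table, overall table and closing list.

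The four wordings therefore reduce to about three thresholds: transformation, unequivocal increase, and any increase.

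Scale, for illustration only:

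- Part 2 LGG patients: 17 (Amendment 11 rationale). One reclassified best response: 1/17 = 5.9 points. Two: 2/17 = 11.8 points.
- With assumed responder counts, 7/17 = 41.2% (exact 95% CI 18.4 to 67.1) against 8/17 = 47.1% (23.0 to 72.2). The same exact method reproduces the Table 5-2 rows checked, such as 4/10 (12.2 to 73.8) and 14/35 (23.9 to 57.9).
- SAP Section 2.1 also pools Part 1 with Part 2 by disease. The number of Part 1 LGG patients is not given. Part 1 enrolled 27, of whom 2 had miscellaneous tumors, so at most 25 were LGG. The pooled denominator then lies between 17 and 17 + 25 = 42, and one patient is worth between 5.9 and 1/42 = 2.4 points.

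The documents do not say how often enhancement rises in isolation.

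**The case against.** The strongest reply is that two of the four statements sit in component tables feeding a composite, so the overall table should be taken to govern. Its last row makes any single criterion enough for PD, which also settles the missing connective at overall level. That last part stands. The rest does not resolve the conflict. No sentence ranks the overall table above the closing list, and it still leaves an equivocal increase without a category. The sentence defining the composite does not list enhancement separately, which implies that it enters through the component tables, and these disagree.

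A second reply is the observation clause: "If there is uncertainty regarding whether there is progression, the patient may continue on treatment and remain under close observation", with PD back-dated if later confirmed. This helps with an equivocal increase, but it names no category for the scan in question and does not choose among the wordings.

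Third, some text may be unavailable. Entries in the overall table carry asterisks with no visible key, possibly lost in extraction, and an imaging manual or reader charter may say more. Nothing here relies on the missing key, but a charter should not have to override the protocol.

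Two stronger readings are tempting. A reader might infer four distinct rules; the non-target table and closing list differ little, and the non-target wording can even be read as requiring an unequivocal increase. A reader might also infer that the response rate turns directly on which line is applied. It does not: a scan with increased enhancement is not CR or PR under any of the statements, even with 60% shrinkage.

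**Conclusion.** The text is internally inconsistent as written and should be reconciled before the RANO-LGG read. The direct effect is on SD and PD counts and on progression dates in that read.

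An effect on the response rate is indirect. It needs an early PD under one wording to end the best-response window before a response that another wording would count. It also assumes that the rule limiting best response to the period before progression applies here; that rule appears in the RECIST part of Appendix 2 and concerns the investigator's assessments. On that assumption each affected patient is worth 5.9 points in Part 2, and less if Part 1 is pooled. How many patients are affected is unknown.

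A reader might infer a threat to the trial's main efficacy result. The documents do not support that. The secondary endpoint is investigator-assessed response (Protocol Section 2), independent review is supportive (Section 5.3.3.3), the older-criteria determinations are retained, and no hypothesis is tested.

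**What to change.** Before the RANO-LGG independent read:

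1. Adopt one enhancement threshold for PD and use identical words in the target table, non-target table, overall table and closing list. The overall table's existing "unequivocal increase" is one candidate; the sponsor should choose and record why.
2. Join the two target-table PD conditions with an explicit or.
3. State the category for an increase below the threshold. If it is SD, edit the SD row of the target table, the SD column of the overall table and the SD list, all of which now bar any increase. The non-CR/non-PD row of the non-target table needs the same edit. The overall table's SD column also requires less than 50% shrinkage, so say how a scan with at least 50% shrinkage and a sub-threshold increase is classed.
4. Report how many time-point and best responses change under the any-increase wording.

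The cost is wording in one appendix and any reader charter, plus one sensitivity count. No new scans are needed. The sponsor must commit to one threshold before the read, and must revise the SD wording as well as the PD wording if sub-threshold increases are to be SD.
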